Efficacy of SD-101 alone (at 0.3 to 3 mg/kg) and in combination with SCH 708974 (1 and 10 mg/kg) was evaluated in a preclinical study in tumor-bearing mice. Results from this study demonstrated up to a 25-fold increase in the apparent potency of SD-101 (Figure 7). Current results suggested no apparent potentiation of SD-101 PD effect (all doses) at 1 mg/kg dose of SCH 708974 under the experimental conditions employed (Figure 7).

[figure not shown]

Figure 7 Efficacy of SD-101 Alone (at 0.3 to 3 mg/kg) and in Combination With Surrogate Mouse Anti-IL-10 mAb SCH 708974 (1 and 10 mg/kg).

Combination of SD-101 with SCH 708974 Resulted in up to 25-fold Increases in the Apparent Potency of SD-101. There was Approximately 90 - 100% Inhibition of IL-10 with 1 mg/kg SCH 708974 and 99 - 100% Inhibition of IL-10 with 10 mg/kg SCH 708974.

Nonclinical safety studies with MK-1966

Current studies included a 4-week intravenous toxicity study with an 8-week treatment-free period in cynomolgus monkeys using doses of 25, 75, and 150 mg/kg/week, an intravenous cardiovascular and respiratory telemetry study in cynomolgus monkeys at 75 mg/kg/dose, and an in vitro tissue cross-reactivity study in normal human tissues. In the repeat-dose toxicity study, inflammation of the large intestine in both sexes in the 75 and 150 mg/kg groups was observed, with one early death in the 150 mg/kg males. Large intestinal inflammation fully resolved by the end of the treatment-free period and there were no clinical or postmortem effects in the 25 mg/kg animals, which was determined as the no-observable effect level (NOEL)/no-observable adverse effect level (NOAEL). The systemic exposure at the NOAEL corresponds to 2-fold predicted human exposure based on 10 mg/kg human dose every 2 weeks. Toxicokinetic measurements showed no sex-related differences in exposure, and systemic exposure increased with increasing dose and with repeated dosing. The mean half-life of MK-1966 in the cynomolgus was 12.7 days. Total IL-10, a marker of target engagement, showed increased serum concentration with systemic MK-1966 exposure. Anti-MK-1966 antibodies were detected in the 75 and 150 mg/kg dose groups and were associated with increased elimination of serum MK-1966 and decreased total IL-10 concentration in some animals by the end of the study. In the single dose cardiovascular telemetry study, there was a lack of nocturnal decrease in blood pressure starting at 12 hours post-dose, a lack of

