4.2.2.3 Maximum Dose/Exposure for This Trial

Based on the current trial design and available safety data from the ongoing lymphoma trial (DV3-LYM-01), the maximum fixed intratumoral dose of SD-101 to be evaluated is 4 mg.

Dose escalations will primarily depend on maximum feasible target engagement subject to safety evaluations. The maximum clinical dose with adequate safety margins is expected to be 700 mg for MK-1966, which is predicted to achieve >90% suppression of IL-10 in one dosing period (96% suppression of IL-10 at C_{max}). Studies in the appropriate safety species (Cynomolgus monkeys) showed no adverse effects at doses where the C_{max} and AUC values were 2.5-fold and 2-fold higher, respectively, relative to the highest human exposure expected at 700 mg.

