In all study Parts, both MK-1966 and SD-101 will be held for the adverse events described below in [Table 7](#).

Table 7 MK-1966 and SD-101 Dose Modification Guidelines for Drug-Related Adverse Events

Toxicity	Hold Treatment For	Timing for Restarting Treatment	Treatment Discontinuation
Diarrhea/Colitis	Grade 2-3	Toxicity resolves to Grade 0-1	Toxicity does not resolve within 12 weeks of last dose or inability to reduce corticosteroid to 10 mg or less of prednisone or equivalent per day within 12 weeks
	Grade 4	Permanently discontinue	Permanently discontinue
AST, ALT, or Increased Bilirubin	Grade 2	Toxicity resolves to Grade 0-1	Toxicity does not resolve within 12 weeks of last dose
	Grade 3-4	Permanently discontinue (see exception below) ^a	Permanently discontinue
Type 1 diabetes mellitus (if new onset) or Hyperglycemia	T1DM or Grade 3-4	Hold SD-101 and MK-1966 for new onset Type 1 diabetes mellitus or Grade 3-4 hyperglycemia associated with evidence of beta cell failure	Resume SD-101 and MK-1966 when patients are clinically and metabolically stable

Toxicity	Hold Treatment For	Timing for Restarting Treatment	Treatment Discontinuation
Hypophysitis	Grade 2-4	Toxicity resolves to Grade 0-1. Therapy with SD-101 and MK-1966 can be continued while endocrine replacement therapy is instituted	Toxicity does not resolve within 12 weeks of last dose or inability to reduce corticosteroid to 10 mg or less of prednisone or equivalent per day within 12 weeks
Hyperthyroidism	Grade 3	Toxicity resolves to Grade 0-1	Toxicity does not resolve within 12 weeks of last dose or inability to reduce corticosteroid to 10 mg or less of prednisone or equivalent per day within 12 weeks
	Grade 4	Permanently discontinue	Permanently discontinue
Hypothyroidism		Therapy with SD-101 and MK-1966 can be continued while thyroid replacement therapy is instituted	Therapy with SD-101 and MK-1966 can be continued while thyroid replacement therapy is instituted
Infusion Reaction	Grade 2 ^b	Toxicity resolves to Grade 0-1	Permanently discontinue if toxicity develops despite adequate premedication
	Grade 3-4	Permanently discontinue	Permanently discontinue
Injection Reaction	≥ Grade 3	Toxicity resolves to Grade 0-1	Toxicity does not resolve within 12 weeks of last dose
Pneumonitis	2	Toxicity resolves to Grade 0-1	Toxicity does not resolve within 12 weeks of last dose or inability to reduce corticosteroid to 10 mg or less of prednisone or equivalent per day within 12 weeks

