5.5.2 Prohibited Concomitant Medications

Subjects are prohibited from receiving the following therapies during the Screening, and Treatment Phases of this trial:

- Immunotherapy not specified in this protocol.
- Antineoplastic systemic chemotherapy or biological therapy. Investigational agents not specified in this protocol.
- Radiation therapy; radiotherapy for symptom management is allowed.
- Live vaccines within 30 days prior to the first dose of trial treatment and while participating in the trial. Examples of live vaccines include, but are not limited to, the following: measles, mumps, rubella, chicken pox, yellow fever, rabies, BCG, and typhoid vaccine. Seasonal influenza vaccines for injection are generally killed virus vaccines and are allowed. However, intranasal influenza vaccines (e.g. Flu - Mist®) are live attenuated vaccines, and are not allowed.

Glucocorticoids for any purpose other than to modulate symptoms from an adverse event. Glucocorticoids must be below 10 mg daily to restart SD-101 and/or MK-1966 dosing. Chronic systemic replacement doses of steroids are allowed. Inhaled steroids for management of asthma are allowed.

Subjects who, in the assessment by the investigator, require the use of any of the aforementioned treatments for clinical management should be removed from the trial. Subjects may receive other medications that the investigator deems to be medically necessary.

There are no prohibited therapies during the Follow-up visits.

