5.7 Rescue Medications & Supportive Care

5.7.1 Supportive Care Guidelines

Subjects should receive appropriate supportive care measures as deemed necessary by the treating investigator. Suggested supportive care measures for the management of adverse events with potential immunologic etiology are outlined below. Where appropriate, these guidelines include the use of oral or intravenous treatment with corticosteroids as well as additional anti-inflammatory agents if symptoms do not improve with administration of corticosteroids. Note that several courses of steroid tapering may be necessary as symptoms may worsen when the steroid dose is decreased. For each disorder, attempts should be made to rule out other causes such as metastatic disease or bacterial or viral infection, which might require additional supportive care. The treatment guidelines are intended to be applied when the investigator determines the events to be related to MK-1966 or SD-101.

It may be necessary to perform conditional procedures such as bronchoscopy, endoscopy, or skin photography as part of evaluation of the event.

- **Diarrhea/Colitis:**

Subjects should be carefully monitored for signs and symptoms of enterocolitis (such as diarrhea, abdominal pain, blood or mucus in stool, with or without fever) and of bowel perforation (such as peritoneal signs and ileus).

- All subjects who experience diarrhea/colitis should be advised to drink liberal quantities of clear fluids. If sufficient oral fluid intake is not feasible, fluid and electrolytes should be substituted via IV infusion. For Grade 2 or higher diarrhea, consider GI consultation and endoscopy to confirm or rule out colitis.
- For **Grade 2 diarrhea/colitis** that persists greater than 3 days, administer oral corticosteroids.
- For **Grade 3 or 4 diarrhea/colitis** that persists > 1 week, treat with intravenous steroids followed by high dose oral steroids.
- When symptoms improve to Grade 1 or less, steroid taper should be started and continued over no less than 4 weeks.

- **Hyperthyroidism or Hypothyroidism:**

Thyroid disorders can occur at any time during treatment. Monitor patients for changes in thyroid function (at the start of treatment, periodically during treatment, and as indicated based on clinical evaluation) and for clinical signs and symptoms of thyroid disorders.

- **Grade 2** hyperthyroidism events (and **Grade 3-4** hypothyroidism):

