7.2.4 Evaluating Adverse Events

An investigator who is a qualified physician will evaluate all adverse events according to the NCI Common Terminology for Adverse Events (CTCAE), version 4.0. Any adverse event which changes CTCAE grade over the course of a given episode will have each change of grade recorded on the adverse event case report forms/worksheets.

All adverse events regardless of CTCAE grade must also be evaluated for seriousness.

For studies in which multiple agents are administered as part of a combination regimen, the investigator may attribute each adverse event causality to the combination regimen or to a single agent of the combination. In general, causality attribution should be assigned to the combination regimen (i.e., to all agents in the regimen). However, causality attribution may be assigned to a single agent if in the investigator's opinion, there is sufficient data to support full attribution of the adverse experience to the single agent.

Table 11 Evaluating Adverse Events

An investigator who is a qualified physician, will evaluate all adverse events as to:

V4.0 CTCAE Grading	Grade 1	Mild; asymptomatic or mild symptoms; clinical or diagnostic observations only; intervention not indicated.
	Grade 2	Moderate; minimal, local or noninvasive intervention indicated; limiting age-appropriate instrumental ADL.
	Grade 3	Severe or medically significant but not immediately life-threatening; hospitalization or prolongation or hospitalization indicated; disabling; limiting self-care ADL.
	Grade 4	Life threatening consequences; urgent intervention indicated.
	Grade 5	Death related to AE
Seriousness	A serious adverse event is any adverse event occurring at any dose or during any use of Sponsor's product that:	
	† Results in death ; or	
	† Is life threatening ; or places the subject, in the view of the investigator, at immediate risk of death from the event as it occurred (Note: This does not include an adverse event that, had it occurred in a more severe form, might have caused death.); or	
	† Results in a persistent or significant disability/incapacity (substantial disruption of one's ability to conduct normal life functions); or	

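### Section 5.7.1 sets a later steroid trigger for Grade 3-4 diarrhea/colitis (more than 1 week) than for Grade 2 (more than 3 days)

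*Combined protocol and SAP*

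**What the plan says.** The diarrhea/colitis entry in section 5.7.1 (Supportive Care Guidelines) has two steroid lines, each labelled by grade.

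- Grade 2: diarrhea/colitis "that persists greater than 3 days, administer oral corticosteroids".
- Grade 3 or 4: diarrhea/colitis "that persists > 1 week, treat with intravenous steroids followed by high dose oral steroids".

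Once symptoms fall to Grade 1 or less, a taper of at least 4 weeks follows. Fluids are advised for everyone, and gastroenterology consultation and endoscopy are to be considered from Grade 2 upward.

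The section is advisory. It opens with "Subjects should receive appropriate supportive care measures as deemed necessary by the treating investigator" and calls the measures that follow suggestions. Section 5.5.2 prohibits "Glucocorticoids for any purpose other than to modulate symptoms from an adverse event", so steroids for adverse-event symptoms are permitted at any time. On study drug, section 5.2.3.1 says "In all study Parts, both MK-1966 and SD-101 will be held for the adverse events described below in" Table 7, where diarrhea/colitis is a hold at Grade 2-3 and permanent discontinuation at Grade 4.

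**The concern.** Guidance graded by severity should not ask for a longer wait as the event gets worse. A site that follows section 5.7.1 as written would start steroids after 3 days for a moderate event and would wait a week for a severe or life-threatening one. Nor does the text say whether the one-week clock restarts when a Grade 2 event worsens to Grade 3.

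The bowel is a relevant organ for this antibody. In the 4-week monkey study (section 4.2.2.2.1), "inflammation of the large intestine in both sexes in the 75 and 150 mg/kg groups was observed, with one early death" at the higher dose. The inflammation resolved off treatment, and there was no effect at 25 mg/kg weekly. Section 4.2.2.3 puts the Cmax and AUC at which no adverse effects were seen at "2.5-fold and 2-fold higher, respectively, relative to the highest human exposure expected at 700 mg", so the AUC margin at the top dose is 2-fold.

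Human experience is thin. Section 4.1.3.1 describes single doses up to 10 mg/kg of MK-7089, which has the same amino acid sequence. The related events it names are mild to moderate oral ulcerations, and colitis is not mentioned. Whether colitis will occur with repeated MK-1966 plus SD-101 is unknown.

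**Working it through.** The plan states no figure to reproduce. The check sets the two triggers side by side, compares them with the rest of the protocol, and works out the delay.

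**1. The two triggers (section 5.7.1)**

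| Event | Steroid step | Written wait |
|---|---|---|
| Grade 2 diarrhea/colitis | Oral | More than 3 days |
| Grade 3-4 diarrhea/colitis | Intravenous, then high-dose oral | More than 7 days |

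Difference: 7 − 3 = 4 days, in the wrong direction for severity. The Grade 2 line cannot be read as covering higher grades. The bullet on gastroenterology consultation, directly before it, extends explicitly to Grade 2 and above; the steroid line does not.

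**2. Other Grade 3-4 toxicities in section 5.7.1 with steroid advice**

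| Toxicity | Wait before steroids at Grade 3-4 |
|---|---|
| Pneumonitis | None; intravenous at once |
| Hepatic | None |
| Hypophysitis | None |
| Hyperthyroidism | None |
| Renal failure or nephritis | None |
| Diarrhea/colitis | More than 7 days |

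(Table 8 lists corticosteroids among the options for acute infusion reactions, also without a wait.)

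**3. Grade definition.** Table 11 in section 7.2.4 defines Grade 4 as "Life threatening consequences; urgent intervention indicated". A trigger of more than a week does not fit that.

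**4. DLT clock.** Under criterion 3 in section 5.2.2, a related Grade 3 non-hematologic event in Cycle 1 is a DLT once it has lasted more than 3 days despite optimal supportive care. The suggested care reaches steroids only after 7 days, so an event at Grade 3 throughout becomes a DLT 7 − 3 = 4 days before the written steroid step.

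**5. What the correction changes**

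- Grade 3 from onset: more than 7 days becomes more than 3 days, so 7 − 3 = 4 days earlier.
- Grade 4: more than 7 days becomes prompt treatment, so up to about 7 − 0 = 7 days earlier.
- Worsening events: let d be the days at Grade 2 before Grade 3. The corrected intravenous step falls max(3, d) days after onset. The present one falls d + 7 days after onset if the clock restarts at Grade 3, or 7 days after onset if it does not.
  - With d = 2, the gain is 2 + 7 − 3 = 6 days with restart and 7 − 3 = 4 without.
  - With d = 5, it is 5 + 7 − 5 = 7 days with restart and 7 − 5 = 2 without.

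The spread in the last case shows that the undefined clock matters as well as the threshold.

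**The case against.** The strongest reply is that this is advisory text with little force. Nothing forbids earlier steroids, both drugs are held or stopped without delay, a specialist may be involved from Grade 2, and serious events reach the sponsor within 24 hours. No endpoint, analysis or dose decision uses this line, and few physicians would withhold steroids for a week from a life-threatening event. All of that stands and limits the harm. It does not explain why the written advice is slowest for the worst grades. Holding drug also does not treat established inflammation, and section 4.2.2.4 cites a long half-life as the basis for dosing every 3 weeks.

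Two possible explanations fall short. The summary of changes says these sections were aligned with the sponsor's required oncology language, which explains origin, not clinical reasoning. Section 5.7.1 asks that infection be ruled out, but for every disorder alike, so this cannot justify 3 days at Grade 2 and 7 at Grade 4.

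The exposed group is also narrow. A subject with more than 3 days at Grade 2 should already be on oral steroids, so a steroid-free gap arises only when Grade 3-4 is reached within about 3 days of onset. That is correct, but escalation to intravenous treatment after worsening still carries the one-week trigger.

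Finally, the 3-day Grade 3 threshold is not a figure the protocol supplies for intravenous treatment, and the other organs would support no wait at all. This is fair. The exact day is a clinical choice for the sponsor; the wording proposed is an upper limit and leaves earlier treatment open.

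**Conclusion.** The concern holds. The steroid triggers for diarrhea/colitis are in the wrong order by severity, by 4 days, and nothing in the protocol explains it. The delay in the written step is 4 days for an event at Grade 3 from onset and up to about 7 days for Grade 4. The Grade 4 figure is a maximum read from the text, not a prediction of practice.

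The conclusion concerns the written trigger only and assumes a site that follows it. Earlier treatment is permitted, and the drug holds are not delayed. The documents give no colitis rate, so the number of subjects affected cannot be estimated. This should be corrected: it is a safety instruction about a toxicity seen in the drug's own animal data.

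**What to change.** In section 5.7.1, replace the Grade 3-4 diarrhea/colitis line with two:

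- *Grade 4 diarrhea/colitis: treat promptly with intravenous steroids, then high-dose oral steroids, once infection has been considered.*
- *Grade 3 diarrhea/colitis: start intravenous steroids, then high-dose oral steroids, no later than when the event has lasted more than 3 days, counted from onset at Grade 2 or higher.*

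The second line also settles the clock for events that worsen. If the sponsor prefers no wait at Grade 3, as for the other organs, that would also remove the inversion.

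The cost is one line becoming two. Section 5.2.2 need not change, and few or no new DLTs are expected: in Cycle 1, related Grade 4 events (criterion 1) and related Grade 3 events lasting more than 3 days despite optimal care (criterion 3) already count.

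One path deserves notice. A mixed event with 3 days or less at Grade 3 but more than 3 days in all could newly receive steroids and the taper of at least 4 weeks. Section 5.5.2 requires glucocorticoids below 10 mg daily before restarting, and criterion 8 makes a Cycle 2 delay of more than 2 weeks for drug-related toxicity a DLT. Such a subject would start steroids no earlier than the Grade 2 line already asks for an event that never worsened.

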5.8 Diet/Activity/Other Considerations

5.8.1 Diet

Subjects should maintain a normal diet unless modifications are required to manage AEs such as diarrhea, nausea or vomiting.

5.8.2 Contraception

MK-1966 and SD-101 may have adverse effects on a fetus in utero. Furthermore, it is not known if either drug has transient adverse effects on the composition of sperm. Non-pregnant, non-breast-feeding women may be enrolled if they are considered highly unlikely to conceive.

Female subjects will be considered of non-reproductive potential if they are either:

- (1) postmenopausal (defined as at least 12 months with no menses without an alternative medical cause; in women < 45 years of age a high follicle stimulating hormone (FSH)

level in the postmenopausal range may be used to confirm a post-menopausal state in women not using hormonal contraception or hormonal replacement therapy. In the absence of 12 months of amenorrhea, a single FSH measurement is insufficient.);

OR

(2) have had a hysterectomy and/or bilateral oophorectomy, bilateral salpingectomy or bilateral tubal ligation/occlusion, at least 6 weeks prior to screening;

OR

(3) has a congenital or acquired condition that prevents childbearing.

Female and male subjects of reproductive potential must agree to avoid becoming pregnant or impregnating a partner, respectively, while receiving study drug and for 120 days after the last dose of study drug by complying with one of the following:

(1) practice abstinence[†] from heterosexual activity;

OR

(2) use (or have their partner use) acceptable contraception during heterosexual activity.

Acceptable methods of contraception are[‡]:

Single method (one of the following is acceptable):

- intrauterine device (IUD)
- vasectomy of a female subject's male partner
- contraceptive rod implanted into the skin

Combination method (requires use of two of the following):

- diaphragm with spermicide (cannot be used in conjunction with cervical cap/spermicide)
- cervical cap with spermicide (nulliparous women only)
- contraceptive sponge (nulliparous women only)
- male condom or female condom (cannot be used together)
- hormonal contraceptive: oral contraceptive pill (estrogen/progestin pill or progestin-only pill), contraceptive skin patch, vaginal contraceptive ring, or subcutaneous contraceptive injection

For this trial, male subjects will be considered to be of non-reproductive potential if they have azoospermia (whether due to having had a vasectomy or due to an underlying medical condition).

[†]Abstinence (relative to heterosexual activity) can be used as the sole method of contraception if it is consistently employed as the subject's preferred and usual lifestyle and if considered acceptable by local regulatory agencies and ERCs/IRBs. Periodic abstinence (e.g., calendar, ovulation, sympto-thermal, post-ovulation methods, etc.) and withdrawal are not acceptable methods of contraception.

‡If a contraceptive method listed above is restricted by local regulations/guidelines, then it does not qualify as an acceptable method of contraception for subjects participating at sites in this country/region.

Subjects should be informed that taking the study medications may involve unknown risks to the fetus (unborn baby) if pregnancy were to occur during the study. In order to participate in the study subjects of childbearing potential must adhere to the contraception requirement (described above) from the day of study medication initiation (or 14 days prior to the initiation of study medication for oral contraception) throughout the study period up to 120 days after the last dose of trial therapy. If there is any question that a subject of childbearing potential will not reliably comply with the requirements for contraception, that subject should not be entered into the study.

